OFFICIAL TITLE OF STUDY: Targeting Burdensomeness Among Clinic Referred Youth

NCT NUMBER: 03781037

DATE: 02-13-2020

PROTOCOL

Suicidal ideation is prevalent in youth: 17.7% of high school students seriously considered a suicide attempt and 14.6% made a specific plan for suicide in the past 12 months¹. Suicidal ideation also is a strong predictor of future suicide attempts and suicide²⁻³. Despite decades of research and intervention, the rates of suicidal ideation and suicide in youth continue to rise in recent years¹. There is critical need for novel intervention targets to prevent and reduce suicidal ideation in youth. To address this critical need, the Sponsor ([name]) is developing and evaluating a novel, brief psychosocial treatment module targeting perceived burdensomeness towards others that can be embedded within existing psychosocial treatments for youth. This F31 project leverages the sponsor's clinical trial to allow the applicant to collect additional qualitative and quantitative data on the module (described below) and gain clinically relevant research experience by assisting the sponsor in the development of the module, implementation of the trial, and analysis of additional data.

Substantial research documents perceived burdensomeness towards others as a risk factor for suicidal ideation⁴, including in youth⁵⁻⁶, highlighting the potential promise of perceived burdensomeness as an intervention target to prevent or reduce suicidal ideation. Only one study, conducted by the Sponsor, has examined an intervention targeting perceived burdensomeness in youth⁷. In 80 youth ages 13 to 19 years, subjects who completed two brief online modules targeting perceived burdensomeness showed significantly lower levels of perceived burdensomeness at POST compared with subjects who received online psychoeducation. This initial finding is exciting because it demonstrates a brief psychosocial intervention can successfully target and reduce perceived burdensomeness when administered online. However, tempering this excitement is the finding that approximately 50% of subjects did not complete the online modules. Thus, there is need to enhance engagement with treatment, as well as expand intervention approaches to clinic-referred populations at higher risk of suicidal behaviors than community-based populations.

One strategy for enhancing engagement and completion of a brief intervention targeting perceived burdensomeness is to embed it within existing psychosocial treatments for youth psychopathology (e.g., cognitive-behavioral therapy [CBT] for youth anxiety disorders). Consistent with a modular CBT approach⁸, this strategy would enable clinicians to select and employ a brief intervention module when youth clients demonstrate thoughts of being a burden on others, with minimal disruption to the ongoing intervention protocol.

The purposes of this project are to (1) develop a novel, brief psychosocial intervention module (the GIVE module) targeting perceived burdensomeness towards others that can be embedded within existing CBT protocols for youth internalizing problems, and then (2) collect data relevant to the timing of reductions in perceived burdensomeness. The following aims will be pursued with N=30 clinic referred youths ages 10 to 17 who are receiving outpatient CBT for anxiety or depression.

Aim 1: Develop a manualized module targeting perceived burdensomeness to be used as an adjunct to existing psychosocial treatments. The GIVE module will consist of one core intervention session involving the youth and a parent (approx. 50 minutes) and one follow-up discussion of homework completion (approx. 10 minutes).

Aim 2: In an open trial, examine adherence and satisfaction with the GIVE module. Adherence, operationalized as provider fidelity and integrity, will be assessed by coding recorded session content. Youth and parent satisfaction will be assessed using the Client Satisfaction Questionnaire.

Aim 3: In an open trial, demonstrate reductions in youth levels of perceived burdensomeness. Perceived burdensomeness will be assessed at pretreatment (PRE), midtreatment (MID; i.e., CBT session 6), every treatment session, and posttreatment (POST). We expect that perceived burdensomeness will be significantly lower at POST relative to MID (i.e., CBT session 6, immediately before beginning the GIVE module).

APPROACH

General overview. Following parental consent and youth assent, parents and youths will be administered interviews and questionnaires as part of PRE assessment to determine eligibility for this study (see Inclusion/Exclusion criteria). Eligible youths will be allocated to a 12-session CBT protocol with an additional module targeting perceived burdensomeness to be administered during CBT session 6. Youth participants' levels of perceived burdensomeness will be assessed weekly at the beginning of each session of the CBT protocol and again at a POST assessment one week after the final CBT session.

Participants. N=30 youths ages 10 to 17 years will be recruited upon entry into clinical services for anxiety and/or depression.

Inclusion criteria. To be included in this study, youth must: 1) be between ages 10 to 17 years old; 2) meet for a primary DSM-V diagnosis of an anxiety disorder, persistent depressive disorder, or major depressive disorder; 3) score ≥ 4 on the youth self-report Interpersonal Needs Questionnaire- Perceived Burdenomeness

Scale at PRE and again at CBT session 5; and 4) if youth have ADHD, tics, or impulse control problems, those disorders must receive an impairment rating no greater than 4 ('Moderate') on the 0–8 point scale on the Anxiety Disorders Interview Schedule Child/Parent versions (ADIS-C/P).

Exclusion criteria. Youth will be excluded from this study if they: 1) meet diagnostic criteria for Psychotic Disorders, Autism Spectrum Disorder or Intellectual Disability, 2) show high risk of imminent self-injurious behaviors, 3) are involved currently in another psychosocial treatment; 4) are not living with a primary caregiver who is legally able to give consent for the youth's participation, or 5) are a victim of previously undisclosed abuse requiring investigation or ongoing supervision by the Department of Social Services.

GIVE module. The GIVE module will include three components: (1) in-session cognitive restructuring, introduced by a brief rationale and psychoeducation; (2) a home assignment to be completed by youth; (3) a parent component providing psychoeducation on burdensomeness that sets up a brief parent-child relationship task. Table 1 provides an outline of the core session of the module, and the follow-up session. The module will be briefly introduced to youth with a rationale outlining the importance of addressing specific negative beliefs that may appear as secondary to the presenting problem but which are nonetheless critical to address, particularly perceived burdensomeness; this brief rationale will be followed by psychoeducation on what fosters this negative belief and outcomes related to this belief (overall introduction is approximately 5 minutes). The first major component of the GIVE module (during the subsequent 15 minutes of session 6), in-session cognitive restructuring with the youth only, consists of identifying negative thoughts (i.e., burdensomeness) using real-life examples and then collaboratively evaluating cognitions of burdensomeness using techniques such as reality testing and cost-benefit analysis¹⁸, with the aim of developing and shaping more adaptive cognitions. Cognitive restructuring will be conducted in a developmentally appropriate manner based on empirically-supported CBT protocols for youth. Consistent with the priority of minimal disruption to ongoing treatment, session 6 is an ideal session to introduce the module because it will leverage existing CBT skills covered earlier in treatment (i.e., cognitive restructuring).

Table 1. Module Outline

Core Session (session 6 of CBT protocol)	
 5 minutes: Rationale for module and psychoeducation on burdensomeness 15 minutes: Cognitive restructuring of burdensomeness 15 minutes: Planning home behavioral assignment 5 minutes: Psychoeducation on parental acceptance 10 minutes: Parental acceptance activity (positive qualities and ways to show acceptance lists)
Follow-up Session (session 7 of CBT protocol)	
 5 minutes: Discussion of home behavioral assignment 5 minutes: Wrap-up Resume ongoing CBT

The second component of the GIVE module is a home behavioral assignment to be planned in the subsequent 15 minutes of session 6. This home assignment is based on a brief online intervention developed by the sponsor⁷. In this brief at-home assignment, youths will identify one family member on whom they believe themselves to be a burden, and will design an activity to contribute to the well-being of that family member⁷ (usually the mother). This home assignment will be collaboratively planned during the session, including identification of barriers to completing the assignment and problem-solving aimed at improving completion of the assignment. Youths will already have been completing home assignments during previous CBT sessions and so the current home assignment should not impose new burden in terms of planning or execution. There will also be a brief discussion of this task in the beginning of the following session for approximately 5 minutes.

The third component of the GIVE module is a brief in-session parent-child relationship component. Unlike the first two components, the entirety of this component is done with both the youth and the parents present in the subsequent 15 minutes of session 6. This component begins with brief psychoeducation for the parent explaining parental acceptance and its implications in the context of perceived burdensomeness. Then, the parent will devise two lists: one that highlights the positive qualities of the child, and a second that includes ways that the parent can show acceptance and warmth. The inclusion of the third component is driven by research indicating that low parental acceptance fosters negative cognitive styles, and forthcoming research from our team indicating that low parental acceptance is significantly associated with youth perceptions of burdensomeness towards others¹⁸. There will also be a brief 5 minute wrap-up which encompasses review of the module and prevention (i.e., discussing the use of the module tools in forthcoming situations and experiences).

Measures.

Primary Outcome.

Interpersonal Needs Questionnaire- Burdensomeness Scale (INQ10-PB). The INQ10 is a widely used self-rated measure of perceived burdensomeness and thwarted belongingness. The burdensomeness subscale (INQ10-PB) consists of 6 Likert-type items. Prior research supports the convergent validity and internal consistency of the subscales in youth^{5, 20}.

Secondary Outcomes.

The Child and Parent's Report of Parental Behavior Inventory (CRPBI/PRPBI- warmth/acceptance subscale). The CRPBI/PRPBI are 30-item youth-rated and parent-rated measures of perceived parental behavior²¹. The warmth and acceptance subscale consists of 10 items of the CRPBI/PRPBI, with subscale scores ranging from 10 to 30, and higher scores representing higher levels of parental warmth and acceptance.

The Screen for Child Anxiety Related Emotional Disorders (Child Version and Parent Versions; SCARED-C/P). The SCARED-C/P is a 41-item youth-rated and parent-rated measure of youth anxiety symptoms²². Items are rated on a 3-point likert scale ranging from “not true or hardly ever true” to “very true or often true”.

The Children's Depression Inventory 2- Child and Parent Version (CDI 2-C/P) The CDI 2-C/P is a widely used measure of youth depressive symptoms, with a 28-item child-rating version and a 17-item parent-rating version²⁴.

The Client Satisfaction Questionnaire-8 (CSQ-8) The CSQ-8 is an 8-item rating scale of client satisfaction with treatment administered²⁶.

Anxiety Disorders Interview Schedule – Child/Parent-V (ADIS-C/P-V). The ADIS-C/P is a widely used semi-structured diagnostic interview for youth and parents. It will be used to determine inclusion/exclusion criteria.

STATISTICAL ANALYSIS PLAN

Data management protocols will be used to ensure data integrity. Missing values will be estimated using full information maximum likelihood where applicable. A Holm modified Bonferroni correction will be used to control experiment wise error rate. We will examine variables measured at PRE, including demographics, symptom severity, parental warmth, and diagnostic status (presence of an anxiety or depressive disorder) for possible inclusion as covariates in the analyses.

Aim 1: Develop a manualized module targeting perceived burdensomeness to be used as an adjunct to existing psychosocial treatments. No statistical analyses will be needed to address this aim.

Aim 2: In an open trial, examine adherence and satisfaction with the GIVE module. Adherence will be examined through descriptive statistics of therapist adherence to the GIVE module protocol. Youth patient and parent satisfaction will be examined using total mean scores and frequencies of item responses on the CSQ-8.

Aim 3: Demonstrate reductions in youth levels of perceived burdensomeness. Reductions in levels of perceived burdensomeness will be examined using two approaches. In the first, a paired samples t-test will be conducted to examine changes in mean scores from MID (i.e., session 6 INQ10-PB score) to POST. A priori power analysis for the paired-samples t-test indicated that N=27 would provide sufficient power to detect a medium effect size, thus the current study would have adequate power. In the second, segmented regression analysis will be conducted by the applicant to preliminarily gain insight into the timing and maintenance of changes in levels of perceived burdensomeness. The segmented regression method is a powerful analysis for a quasi-experimental, interrupted time-series designs²⁸⁻²⁹, recommended for small samples²⁸. In segmented regression analysis, session to session assessments of perceived burdensomeness will be used to examine the slopes in perceived burdensomeness before and after intervention in CBT session 6. The intervention effect is examined by statistically comparing the PRE and POST intervention slopes. In an interrupted time-series design, it is recommended that observations be equally balanced between pre intervention and post intervention (e.g., 6 observations before and after), and for the PRE assessment variability to be reduced (e.g., only selecting youth with higher PB for the study) to maximize power²⁸. For this reason, there are six assessment points (administrations of INQ10-PB) planned prior to and after the administration of the module for a total of 12 observations, and only youth with elevated PB will be recruited (i.e., variability reduction). The segmented regression analysis is intended to be preliminary to gain insight into the timing of changes, and as such, may be underpowered by design.

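### The session 5 inclusion score removes youths from the sample on the outcome itself, does not fit the overview's eligibility at PRE, and leaves the pre-module slope in the segmented regression conditioned on not having improved below 4

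*Combined protocol and SAP*

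**What the plan says.** Approach, Inclusion criteria, item 3: youths must "score ≥ 4 on the youth self-report Interpersonal Needs Questionnaire- Perceived Burdenomeness" "Scale at PRE and again at CBT session 5". The list is introduced as conditions for being in the study, not for receiving the GIVE module.

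Approach, General overview: parents and youths are "administered interviews and questionnaires as part of PRE assessment to determine eligibility for this study". Then "Eligible youths will be allocated to a 12-session CBT protocol" with the module at session 6, and burdensomeness is "assessed weekly at the beginning of each session of the CBT protocol and again at a POST assessment". Session 5 has no role in this account.

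The project's second purpose is to "collect data relevant to the timing of reductions in perceived burdensomeness". The Statistical Analysis Plan, Aim 3, has two analyses. One is a paired t-test of "changes in mean scores from MID (i.e., session 6 INQ10-PB score) to POST". The other is a segmented regression comparing slopes before and after session 6, intended to "preliminarily gain insight into the timing and maintenance of changes in levels of perceived burdensomeness". Selection of elevated youths is justified there by lower variability at PRE; no reason is given for repeating the check at session 5. No analysis population is defined, and the full information maximum likelihood sentence is not linked to youths who fail the repeat.

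**The concern.** By session 5 a youth has consented, passed PRE, started CBT and supplied several primary-outcome scores. A score below 4 then fails an inclusion criterion. This is selection on the outcome, made inside the pre-intervention segment of an interrupted time series.

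The segmented regression rests on comparing the trend before the module with the trend after it. If the earlier trend is estimated only in youths whose score had not dropped below 4 by its fifth session, it is pulled upward near its end. Nothing comparable is done to the later trend. The comparison can then show a faster fall after session 6 that the module did not cause. The plan also cannot say how many youths improved below the cut under CBT alone, which bears directly on a project about timing. Finally, it is unclear whether the 30 youths are counted before or after the session 5 check.

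**Working it through.** **1. The plan's own figure.** N=27 is given for a medium effect, without alpha, sidedness or power. An exact noncentral-t calculation for a paired test with d = 0.5 and one-sided alpha 0.05 gives power 0.812 at N=27, the smallest N reaching 80%. The figure reproduces on those assumptions (a two-sided test would need 34).

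**2. What the count means.** The share f of PRE-eligible youths below 4 at session 5 is not in the documents, so a range is assumed. If 30 is counted at entry, 30 x (1 - f) remain. If 30 is counted after the check, 30/(1 - f) must start.

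| f | Left from 30 | One-sided power, d = 0.5 | Starters needed for 30 |
|---|---|---|---|
| 20% | 24 | 0.77 | 38 |
| 30% | 21 | 0.72 | 43 |
| 40% | 18 | 0.65 | 50 |
| 50% | 15 | 0.58 | 60 |

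**3. Effect on the slopes, in SD units.** All parameters are assumed. Score at time t (PRE = 0, sessions 1-12, POST = 13) = person level (variance 0.6) - decline x t/13 + independent error (variance 0.4). The mean decline from PRE to POST is 0.3, 0.6 or 1.0 SD, with between-youth SD 0 or 0.5. The same cut applies at PRE and session 5, at the mean or 0.5 SD below it. The module does nothing. This makes 12 settings.

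- Between 22% and 46% of PRE-eligible youths fail at session 5.
- Example: decline 0.6, common to all, cut at the mean. The true slope is -0.6/13 = -0.046 per session before and after session 6. Fitted over sessions 1-6 it is -0.046 in all PRE-eligible youths and -0.021 in those kept. The later slope in those kept is still -0.046, so the false difference is -0.046 - (-0.021) = -0.025.
- Over the 12 settings the false difference is about -0.015 to -0.030 SD per session in those kept, and about 0 in all PRE-eligible youths.

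Mechanism in the example: in a six-point least-squares slope, session 5 has weight (5 - 3.5)/17.5 = 0.086. A flattening of 0.025 therefore corresponds to a mean session 5 error of 0.025/0.086 = 0.29 SD in those kept, which is the selected part of the score.

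**4. A second, milder set of assumptions.** Score points with mean 8, between-youth SD 5, occasion SD 2 to 3, slope 0 to -0.5 per session, slope SD 0 to 0.5, cut at 4, inert module. The check removes 12% to 28%. The sessions 1-6 slope goes from -0.30 to -0.19 in one setting and from -0.50 to -0.32 in another. The false difference is -0.025 to -0.071 points per session. Dividing by the total SD gives -0.025/√(25 + 4) = -0.005 to -0.071/√(25 + 9) = -0.012 SD per session: the same direction, but smaller.

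**5. Dependence on the segment.** Step 3 and the range in step 4 take sessions 1-6 as the six pre-module points, since session 6 is scored before the module. If PRE to session 5 is used instead, the step 4 difference in those kept runs from -0.065 to 0.002 points. In all PRE-eligible youths it is +0.04 to +0.09, because regression to the mean from the PRE cut steepens the early slope. PRE should therefore be left out of the comparison slope.

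**6. MID to POST.** MID is session 6, one week after the selecting score. In step 4 the mean change was 2.10 with and without the session 5 check when slopes were common, and 1.68 against 2.09 when they varied. It is not inflated.

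**The case against.** The strongest objection is that the documents never say these youths leave. A reader might infer that they drop out and are not followed, and that everyone whose burdensomeness fell early is discarded. Neither is supported. The text is silent on what follows a low session 5 score, the overview points to continued weekly and POST assessment, and youths who fell but stayed at 4 or above remain. What stands is that a criterion for being in the study is failed, with no stated handling.

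A reader might also infer that the pre-module fall is understated by 12-28%, from the PRE-to-session-6 fall in all enrolled youths against those kept (0.59 versus 0.48 SD in the step 3 example). That benchmark is unsound. The true decline there is 0.6 x 6/13 = 0.28 SD, so both figures are inflated by regression to the mean from the PRE cut, and the kept figure is the closer one. It is not used here.

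The cut may exclude nobody. The six items have no stated anchors or scoring; scored from 1 and summed, the minimum is 6. This stands as a condition on the whole point, although asking for the score twice suggests that some are expected to fail.

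The segmented regression is declared preliminary and possibly underpowered, and treating youths who are still elevated fits the module's stated use. Both limit the importance of the point. But low power excuses imprecision, not a bias in one direction, and the module's intended use does not require losing scores already collected.

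**Conclusion.** The point holds in this form. Criterion 3 and the General overview disagree on when eligibility is settled. Read as written, criterion 3 selects on the primary outcome after treatment has begun, with no count, analysis set or report for those who fail it. If the cut excludes anyone, the planned slope comparison can lean towards the module when the module is inert: about -0.015 to -0.030 SD per session under the assumptions of step 3, and about -0.005 to -0.012 under the milder set. The direction is the same in all settings when sessions 1-6 form the pre-module segment. The size is illustrative, because the documents give no score distribution, reliability or pass rate, and errors are assumed independent between sessions. The paired MID-to-POST test is not shown to be inflated; it simply applies to youths still elevated after the early CBT sessions. The change should be made, because it concerns a planned analysis and a stated purpose.

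**What to change.** Reconcile criterion 3 with the General overview, and state the status of a youth who is eligible at PRE, starts CBT and scores below 4 at session 5. Who receives the module is for the sponsor to settle in doing so. State how the INQ10-PB is scored. Then:

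- keep the PRE and session 1-5 scores already collected for every youth eligible at PRE who starts CBT;
- report the number and proportion below 4 at session 5;
- beside the planned segmented regression, report the sessions 1-5 slope in all these youths, leaving out PRE;
- state whether N=30 is counted before or after session 5;
- limit the MID-to-POST and slope conclusions to youths still at 4 or above at session 5.

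Where youths below 4 continue in the clinic's CBT, later INQ10-PB scores may be shown descriptively only. They are not a control group and cannot prove that early reductions last: under the step 3 model, 33-54% of those failing at session 5 are back above the cut at session 6, largely through noise.

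The cost is protocol wording, a little more analysis, and a 6-item form per session if later scores are collected. The slope comparison may look less favourable to the module.

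### The Aim 3 MID to POST paired t-test uses only youth with both scores, and the SAP names no model through which its FIML rule or the weekly scores would reach that contrast

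*Combined protocol and SAP*

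**What the plan says.** In the Statistical Analysis Plan, the first approach to Aim 3 is that "a paired samples t-test will be conducted to examine changes in mean scores from MID (i.e., session 6 INQ10-PB score) to POST". The power calculation belongs to this test: "A priori power analysis for the paired-samples t-test indicated that N=27 would provide sufficient power to detect a medium effect size". Enrolment is set under Participants: "N=30 youths ages 10 to 17 years will be recruited upon entry into clinical services".

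On missing data, the opening paragraph of the SAP has one sentence: "Missing values will be estimated using full information maximum likelihood where applicable". It does not say which analyses it covers, and the Aim 3 text does not mention missing scores. No drop-out rate, missing-data assumption or sensitivity analysis is given.

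Under General overview, burdensomeness is to be "assessed weekly at the beginning of each session of the CBT protocol and again at a POST assessment". Six weekly scores (sessions 7 to 12) therefore lie between the two that the t-test uses. They enter only the second approach, in which "session to session assessments of perceived burdensomeness will be used to examine the slopes" before and after session 6. The plan presents that approach as preliminary and says that it "may be underpowered by design".

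**The concern.** A paired t-test drops every youth without a POST score and has no likelihood step through which FIML could enter. If leaving after session 6 depends on how burdensome a youth feels, those who remain are a selected group and their mean change is biased. The weekly scores show how each youth was doing before leaving, yet the contrast on which the expected Aim 3 result rests does not use them. There is no control arm, so bias in this change passes straight into the Aim 3 result.

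The FIML sentence also leaves room for different analyses. One analyst could run the t-test on completers, another could fit FIML to the two scores, and a third could fit it to all the weekly scores. As shown below, these can give different answers.

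**Working it through.** **1. The plan's own figure.** The power of a paired t-test comes from a noncentral t with n-1 df and noncentrality d_z × √n. A medium effect is taken as d_z = 0.5, which is an assumption because the plan gives no number. At n = 27 the noncentrality is 0.5 × √27 = 2.60. With one-sided alpha 0.05, power is 81.2% (79.8% at n = 26), so N=27 for 80% power is reproduced. With two-sided alpha 0.05, power is 70.6% and 34 would be needed. The documents state neither alpha nor sidedness. The margin for lost pairs is (30-27)/30 = 10%.

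**2. Where the bias comes from.** Let D be POST minus session 6, and p the share lost. Then

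completers' error = mean D of completers - mean D of all = -p × (mean D of those lost - mean D of completers).

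- Random loss: the gap is zero, so there is no bias.
- Youth who do not improve leave: the lost have higher D, the error is negative, and the reduction is overstated.
- Youth with high session 6 scores leave: they would tend to fall further, the error is positive, and the reduction is understated.

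An error of -0.16 at p = 0.20 means a gap of 0.16/0.20 = 0.8 SD. An error of 0.04 at p = 0.10 means a gap of 0.4 SD.

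**3. Simulated size when drop-out follows observed scores.** All inputs here are assumptions.

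- Eight visits (sessions 6 to 12 and POST), session 6 SD 1, true change -0.35.
- Twelve data models. Eight combine random intercept, random slope and AR(1) residual. Four do not match the fitted covariance: sudden gains, shrinking SD, growing SD, and a rounded score floored at 0 with the entry rule applied (true change -0.45).
- Drop-out is monotone and logistic. It follows the last score, lack of improvement, or the session 6 score, with coefficient 0.5, 1 or 2 per SD (odds ratio 1.6, 2.7, 7.4).
- 60,000 youth per model.

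Errors are estimate minus full-data change, in session 6 SDs:

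| Loss; dependence per SD | Completers | Weekly-score likelihood model |
|---|---|---|
| 10%; 0.5 | -0.04 to +0.04 | within 0.003 |
| 10-20%; 0.5-1 | -0.16 to +0.14 | -0.006 to +0.008 |
| up to 30%; up to 2 | -0.36 to +0.29 | -0.015 to +0.022 |

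In the middle row the model is closer in 140 of 144 settings. At N=30 with REML (20% loss, 1 per SD, random or observed-score loss), the model errs by -0.018 to +0.008 and completers by -0.17 to +0.14; the RMSE ratio, model to completers, is 0.80-1.02. At 10% loss and 0.5 per SD (one data model), RMSE is 0.18-0.19 for both.

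**4. FIML on two scores only.** In a separate simulation, the true change was -0.50 SD of the differences, dependence was 1.5 per SD, and 24-31% were lost. With drop-out following the last observed level or change, likelihood estimation on session 6 and POST alone gave -0.60 to -0.64. With the weekly scores it gave -0.50 to -0.51. Completers gave -0.47 (level) or -0.67 to -0.69 (change). Two-score FIML can thus be further off than completers.

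**5. False reductions.** With no true change, 20% loss, 1 per SD and a two-sided 5% test (nominal 2.5% in the direction of reduction), the t-test gives:

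- drop-out following lack of improvement: roughly 4-9%
- following the last score: 2-4%
- following the session 6 score: 0.5-2% (conservative)

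The model gave 2.0-2.7% under lack of improvement. At 10% loss and 0.5 per SD the rates were 3.6% (t-test) and 2.4% (model).

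**6. Drop-out that follows unseen scores (10-20% loss, 0.5-1 per SD).** If it follows the current, unrecorded score, the model errs by -0.075 to -0.006 and completers by -0.078 to +0.022. The model is the worse of the two in 36 of 48 settings, by at most 0.026 SD. If it follows the unseen POST score, the model is worse in 35 of 48, by at most 0.038 SD. Its largest error there is 0.113 SD at 10% loss and 0.226 SD at 20%. Divided by the share missing, both give 1.13 SD (0.113/0.10 and 0.226/0.20), the shift in missing POST scores that would undo the error.

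**The case against.** The SAP does have a missing-data rule. It stands ahead of all the aims and can be read to cover this contrast, so a reader who infers a completers-only policy goes beyond the text. That stands. What remains is an ambiguity with consequences, because applying FIML to the two scores does not settle it (step 4).

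Materiality rests on assumed drop-out. That also stands. A reader might take the background statement that "approximately 50% of subjects did not complete the online modules" as a forecast. It concerns self-directed online modules, whereas here the module sits inside clinic CBT to improve completion, and eligible youth are re-checked at session 5. The figure shows only that loss above 10% cannot be ruled out. At 10% loss with weak dependence the two methods are practically equal.

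A reader might also infer that the t-test will overstate the reduction or inflate false positives. Only one of the three observed-score mechanisms clearly does so; another makes the test conservative. The 2.5% benchmark further assumes a two-sided 5% test, whereas N=27 is reproduced only with a one-sided one.

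Finally, the model is not uniformly better. With unseen-score drop-out it is often slightly worse, and at N=30 a covariance parameter reached its boundary in 4-56% of trials. Both stand. They are reasons for a sensitivity analysis and a fallback, and the losses are small beside the gains under observed-score drop-out.

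**Conclusion.** The point holds as a cheap improvement to the SAP, not as a demonstrated error in the result. If drop-out after session 6 depends on observed burdensomeness, the completers' change is biased by about -0.16 to +0.14 session 6 SDs at 10-20% loss and 0.5-1 per SD. A likelihood contrast on the weekly scores reduces this to less than 0.01 SD. These sizes depend on assumed drop-out rates, mechanisms and correlations, none of which the documents give, so confidence in the practical size is medium.

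The change addresses drop-out bias only. It is tempting to see it as a repair for power, but the sampling SD at N=30 is almost the same (0.15-0.29 for the model, 0.16-0.30 for completers). Nor does it allow an open trial without a control arm to attribute the change to the module.

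**What to change.** - Make the Aim 3 test the session 6 versus POST contrast from a REML repeated-measures model with visit categorical and small-sample degrees of freedom. Use all INQ10-PB scores from session 6 to POST for every youth with a session 6 score, and state that this is how FIML applies to Aim 3.
- Prespecify a structured covariance suited to about 30 youth, and a simpler fallback. An unstructured matrix over eight visits has 8 × 9/2 = 36 parameters. Random intercept and slope plus AR(1), falling back to random intercept plus AR(1), is one example and not a requirement.
- Keep the paired t-test as a completers' sensitivity analysis.
- State the missing-at-random assumption and the alpha and sidedness of the test.
- Add a delta-adjusted analysis that shifts missing POST scores upward in steps and reports where the reduction ceases to be significant. Each step moves the contrast by share missing × delta. Steps to about 1.1 SD cover the simulated cases at 10-20% loss and 0.5-1 per SD.

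Cost: SAP wording and some extra analysis work, with no new data. With complete data the model estimate equals the paired mean difference. The downsides to accept are frequent boundary estimates at N=30; a fallback that protects less (-0.042 to +0.023 at 10-20% loss and 0.5-1 per SD, closer than completers in 81% of settings); and often slightly more bias than completers if drop-out follows unseen scores (at most about 0.04 SD at those settings).
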